7.2.2. Primary Analysis of the Primary Endpoint

The proportion of participants who are identified as operationally tolerant with a corresponding two-sided 95% exact binomial confidence interval. This will be analyzed using the ITT and PP samples.

The results will be presented in a table as shown below.

	Total (N = XX)
	n (%)
Proportion Tolerant [1]	X (X.X%)
95% Exact Binomial Confidence Interval	(X.X, X.X)

[1] Subjects who remain off immunosuppression for at least 52 weeks without evidence of rejection and demonstrate histological stability, as determined by a biopsy performed 52 weeks after the completion of immunosuppression withdrawal, are considered tolerant.

7.3. Secondary Endpoints

All secondary endpoints will be analyzed as described in Table 7-2. Mock displays for these results are outlined in the Appendix.

Table 7-2 Table of Endpoints and Analysis Methods

Endpoint	Method	Population
Primary		
The proportion of participants who achieve operational tolerance 52 weeks after completion of immunosuppression withdrawal.	Proportion of participants who achieve operational tolerance 52 weeks after completion of immunosuppression withdrawal with a corresponding two-sided 95% exact binomial confidence interval.	ITT, PP
Secondary		
Safety		
The proportion of participants who develop DSA or de novo anti-HLA antibodies after initiation of immunosuppression withdrawal.	Proportion of participants who develop DSA or de novo anti-HLA antibodies after initiation of immunosuppression withdrawal with a corresponding two-sided 95% exact binomial confidence interval.	ITT, PP
The incidence, severity, and timing of acute rejection, steroid resistant rejection, and chronic rejection.	
Acute Rejection: Incidence will be measured as the proportion of participants who have acute rejection (per Banff criteria) with a corresponding two-sided 95% exact binomial confidence interval.
 
Severity will be measured according to the Banff grade. Acute rejection can be expressed as mild, moderate or severe. This will be summarized descriptively with counts and percentages.
	ITT, PP
	
Steroid Resistant Rejection: Incidence will be measured as the proportion of participants who have steroid resistant rejection (rejection requiring antibody treatment) with a corresponding two-sided 95% exact binomial confidence interval.
 
All steroid resistant rejections are considered severe in nature and nothing further will be summarized.
	
	
Chronic Rejection: Incidence will be measured as the proportion of participants who have chronic rejection (per Banff criteria) with a corresponding two-sided 95% exact binomial confidence interval.
	

	
Severity will be measured according to the Banff grade. Chronic rejection can be expressed as early or late. This will be summarized descriptively with counts and percentages.
 
For all rejection types, timing will be expressed as the time from the initiation of immunosuppression withdrawal to the time of the first biopsy showing acute rejection and will be summarized descriptively.
 
All data presented will use the central read.

The incidence and progression of graft fibrosis in tolerant versus non-tolerant patients.	
Fibrosis will be looked at in two ways—by ISHAK ITT, PP and LAFSc.
 
ISHAK is a measure taken directly from the central pathology read.
 
LAFSc is calculated as the sum of three measures that summarize fibrosis in the portal tract (portal_fibrosis per central read), sinusoids (disse_fibrosis per central read), and centrilobular vein (central_fibrosis per central read).
 
For both ISHAK and LAFSc, a subject will be considered as having graft fibrosis if the score is greater than or equal to 2.
 
Incidence of graft fibrosis will be summarized descriptively with a proportion and corresponding two-side 95% exact binomial confidence interval using Ishak Score and LAFSc, separately, for tolerant and non-tolerant subjects.
 
Change in ISHAK score from baseline biopsy to the last available biopsy will be calculated. Descriptively statistics will be calculated separately for tolerant and non-tolerant subjects. This same process will be repeated for LAFSc.
 
All scores utilized will be from the central read.

The incidence of graft loss.	Proportion of participants who have lost their liver graft with a corresponding two-sided 95% exact binomial confidence interval. ITT, PP
The incidence of all-cause mortality.	Proportion of participants who have died with a corresponding two-sided 95% exact binomial confidence interval. ITT, PP

The incidence of study-related SAEs.	Proportion of study-related SAEs as assessed by the NIAID Medical Monitor with a corresponding two-sided 95% exact binomial confidence interval.	ITT, PP
Efficacy		
The proportion of operationally tolerant subjects who remain free of rejection at 3 years after completing immunosuppression withdrawal.	Proportion of tolerant participants who remain off all IS and free of rejection 3 years after completing immunosuppression withdrawal with a corresponding two-sided 95% exact binomial confidence interval.	Tolerant Subjects
Changes in renal function (defined as estimated GFR calculated by CKD-EPI) in tolerant versus non-tolerant participants at 1, 2 and 3 years after completing immunosuppression withdrawal for tolerant subjects and failure of withdrawal for non-tolerant subjects.	
Baseline eGFR will be calculated from data collected at Visit 0. If Visit 0 data is missing, Visit -1 data will be used. Data collected closest to 1-year post completion/failure, within +/- 2 months, will be used to calculate eGFR at 1. The same process will be followed for 2 and 3-years after completion/failure.
 
eGFR will be calculated using the CKD-EPI equation:
 $\text{GFR} = 141 * \min(\text{Scr}/\kappa, 1)^\alpha * \max(\text{Scr}/\kappa, 1)^{-1.209} * 0.993^{\text{Age}} * 1.018 \text{ [if female]} * 1.159 \text{ [if black]}$ 
Scr: serum creatinine (mg/dL) κ: 0.7 for females and 0.9 for males α: -0.329 for females and -0.411 for males
 
Change in eGFR will be calculated as: 1-year post completion/failure eGFR – baseline eGFR
 
Thus positive value will indicate increase kidney function.
 
Changes will be summarized descriptively by tolerance status.
	ITT, PP
Changes in Quality of Life in tolerant versus non-tolerant participants and in all participants at baseline versus the end of study participation, as measured by the NIDDK Liver Transplantation Database Quality of Life Form.	The questionnaire filled out at Visit 0 will serve as the baseline questionnaire. The questionnaire filled out closest to the end of study participation will serve as the end of study questionnaire. For subjects	ITT, PP

	
with complete follow-up, this will be the questionnaire completed at Visit 208 or Visit 306.
 
The questionnaire will be summarized into five domains as outlined by Bell et al. The domains include measures of disease, psychological status, personal function, social and role function, and general health perception.
 
The change in each domain will be calculated as: Domain Score at End of Study – Domain score at Baseline.
 
The baseline, end of study, and change from baseline domain scores will be summarized descriptively by tolerance status.
 
If the data permits, a spaghetti plot visualizing each component score over time will be produced. Each graph will have two panels—one depicting the tolerant subjects, the other depicting the non-tolerant subjects.
	
Changes in SF-36 (see Appendix 6) in tolerant versus non-tolerant participants and in all participants at baseline versus the end of study participation.	
The questionnaire filled out at Visit 0 will serve as the baseline questionnaire. The questionnaire filled out closest to the end of study participation will serve as the end of study questionnaire. For subjects with complete follow-up, this will be the questionnaire completed at Visit 208 or Visit 306.
 
The SF-36 questionnaire will be scored in accordance with the scoring algorithm (Version 2 scoring algorithm used via quality metric) and summarized with the Physical Component Score (PCS) and Mental Component Score (MCS).
 
The change in the component scores will be calculated as: Component Score at End of Study – Component Score at Baseline.
 
The baseline, end of study, and change from baseline domain scores will be summarized descriptively by tolerance status.
 
If the data permits, a spaghetti plot visualizing each component score over time will be produced. Each graph will have two panels—one depicting the tolerant subjects, the other depicting the non-tolerant subjects.
	ITT, PP

Predictive value and the correlative value of the following parameters with regard to operational tolerance:
 
a. Time post-transplant
 
b. Recipient age
	
A logistic regression model will be utilized to estimate the probability of operational tolerance. Time post-transplant and recipient age will be included in the model as continuous covariates. Odds ratios and 95% confidence intervals will be presented.
	ITT, PP
---	--	---------

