Collectively, these studies suggest that operational tolerance develops in approximately 20% of cases^{6,76-80}. Favorable clinical markers for successful immunosuppression withdrawal in these studies were at least 2 years after transplantation, low incidence of previous AR episodes, non-autoimmune liver disease and minimized immunosuppression in the immediate post-transplant period^{74,75,79,80}. However, none of these

markers could be employed to accurately predict the outcome of weaning strategy. Although this strategy is associated with a high rate of acute rejection (AR), these episodes are mild in the majority of cases and can be easily solved without the need to administer high dose steroids. Frequent monitoring of liver function tests is however required to prevent liver damage from becoming irreversible. Given that rejection often develops in an atypical manner, both for-cause and protocol biopsies should be considered as mandatory because increased blood markers of liver dysfunction (liver enzymes and bilirubin) can occur in the absence of rejection^{7,67,71}, and subclinical rejection with normal liver function tests has also been reported in some patients.

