6.8 MANAGEMENT OF ACUTE REJECTION

Immunosuppression will be reinstated for all participants who experience biopsy-confirmed rejection or presumed rejection. Investigators may treat rejection according to institutional standard. The following however are recommended guidelines based on previous experience in liver allograft immunosuppression withdrawal trials:

- Allograft dysfunction with *no acute rejection or indeterminate for acute rejection*, and without other explanatory diagnosis should be treated at the discretion of the site investigator with reinstitution of the baseline IS (regimen employed before initiation of IS withdrawal). If liver tests do not improve within 4 weeks, repeat biopsy should be considered prior to further escalation of treatment.
- *Mild acute rejection* should be treated initially with reinstitution of baseline IS. If liver tests do not improve within 2 weeks, dose increase or addition of 20 mg oral prednisolone (or equivalent) should be considered. Corticosteroids will be rapidly tapered down over a 4 week period. A second biopsy can be performed at any time at the investigator's discretion.

- *Moderate acute rejection without jaundice and with mild biochemical abnormalities* should be treated with reinstitution of baseline IS and 20 mg oral prednisolone (or equivalent) with rapid taper down of steroid doses over a 4 week period. If liver tests do not improve within 2 weeks, conversion or addition of another agent should be considered prior to corticosteroids. A second biopsy can be performed at any time at the investigator's discretion.
- *Moderate acute rejection with marked biochemical abnormalities and/or jaundice, severe acute rejection, or chronic rejection*, should be treated according to site standard of care. Antibody treatment should be reserved for steroid-resistant acute rejection proven by repeat liver biopsy.

Participants who experience biopsy-confirmed rejection or presumed rejection prior to completing immunosuppression withdrawal will undergo safety follow-up per Appendix 3. If the episode of biopsy-confirmed rejection or presumed rejection occurs after the completion of immunosuppression withdrawal, the participant will continue on post withdrawal follow-up per Appendix 2. If the participant is restarted on immunosuppression therapy, the subject will be followed concurrently on Appendix 4 (except during the duration of the COVID-19 pandemic).

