6.10 LIVER BIOPSY

6.10.1 Types of Biopsies

- Protocol Biopsies

- Participants will undergo liver biopsies at times specified in the schedule of events (see Appendices 1 and 2). These biopsies will be used to monitor liver function, to screen for subclinical rejection, and for mechanistic analyses.
- For-cause Biopsies
 - For-cause biopsies (FCB) will be obtained to confirm suspected rejection following unexplained allograft dysfunction (see Section 6.6 for definition) and all mechanistic assessments listed in Appendix 5 should be performed.

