9.3 SAMPLE SIZE

In order to estimate the proportion of operational tolerance with the desired level of precision, enrollment will continue until 60 participants who meet eligibility criteria are enrolled and initiate immunosuppression withdrawal. If the expected proportion of participants who exhibit operational tolerance is 40%, as demonstrated in a study of adult liver recipients by Alberto Sánchez-Fueyo¹⁵, the exact 95% confidence interval on the proportion of operationally tolerant participants is (27.6%, 53.5%). If the expected proportion of participants who exhibit operational tolerance is 60%, the associated exact 95% confidence interval would be (46.5%, 72.4%). Thus, 60 subjects provide the ability to estimate the proportion of operational tolerance within plus or minus approximately 13%.

To ensure secondary endpoints have sufficient power, additional sample size calculations were performed based on published data from [name] in HCV positive liver recipients in which immunosuppression withdrawal was attempted based on the presence of at least one previously reported signature of operational tolerance (by flow cytometry, peripheral blood V δ 1+/V δ 2+ T cell ratio with 82% sensitivity, 53% specificity, 67% positive predictive value, 73% negative predictive value; by real-time PCR, PBMC with 93.33% sensitivity, 93.79% specificity, 93.33% positive predictive value, 93.75% negative predictive value in a retrospective cohort of 28 tolerant, 33 non-tolerant recipients). Of 34 patients in whom immunosuppression was attempted, 17 were successfully withdrawn. Tolerance was significantly associated with an expansion of exhausted PD1/CTLA4/2B4 positive, HCV reactive (IFN γ + following HCV peptide stimulation) circulating CD8+ T cells.

Correlation of CD8+IFN γ +CTLA4+PD1+2B4+ marker with tolerance

Based on these data, members of the ITN performed the following sample size estimate analysis for this trial based on the following assumptions: 80% and 90% power, 5% level of significance.

For CD8+IFN γ +CTLA4+PD1+2B4+

The mean difference expected in the two groups is -0.1155. The pooled standard deviation is 0.152.

Power	Tolerant Proportion	Non-Tolerant Proportion	Total N	Tolerant N
0.808	0.6	0.4	60	36
0.907	0.6	0.4	80	48
0.796	0.5	0.5	56	28
0.904	0.5	0.5	76	38
0.808	0.4	0.6	60	24
0.907	0.4	0.6	80	32
0.818	0.3	0.7	70	21
0.903	0.3	0.7	90	27

Analyses involving all other biomarkers will be exploratory in nature.

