APPENDIX 3. SCHEDULE OF EVENTS – SAFETY FOLLOW-UP

IMPORTANT NOTE: For the duration of the COVID-19 pandemic, follow the COVID-19 Modified Appendix 3-C instead.

Safety Follow-up Weeks ¹	0	13	26	52	104	156
Visit Number ²	301 ^{3,4}	302	303	304	305	306
General Assessments						
Limited Physical Exam	X	X	X	X	X	X
Vital signed including weight	X	X	X	X	X	X
Quality of Life Questionnaires	X		X	X	X	X
Status Change since prior visit ⁵	X	X	X	X	X	X
Telephone consultation ⁶	X					X
ECG			Prior to restarting tacrolimus if on MMF monotherapy ⁷			
Local Clinical Laboratory Assessments						
LFTs ⁸		Every 4 weeks		Every 8 weeks		Every 12 weeks
CBC w/differential	X	X	X	X	X	X
Comprehensive metabolic panel, includes LFTs	X	X	X	X	X	X
Mechanistic Laboratory Assessments						
Frozen PBMC collection	X		X	X	X	X
Serum collection	X		X	X	X	X
Whole blood collection	X		X	X	X	X
Urine pellet collection	X		X	X	X	X
Fecal collection	X		X	X	X	X

¹ The assessments outlined in Appendix 3 should be completed for all participants who initiated but did not complete immunosuppression withdrawal. Follow-up should begin within 2 weeks of the date of immunosuppression withdrawal failure (see section 3.1.3.5).

² If a for-cause liver biopsy is needed, follow all assessments specified in Appendix 5. If the for-cause biopsy occurs within 8 weeks prior to a scheduled protocol visit, complete all clinical and mechanistic assessments listed in Appendix 5 at the time of the for-cause biopsy. The for-cause biopsy visit will take the place of the scheduled protocol visit.

³ If a for-cause liver biopsy visit took place within 8 weeks of visit 301, all mechanistic assessments listed in Appendix 5 at the time of the for-cause biopsy visit should be completed in lieu of mechanistic assessments listed for visit 301.

⁴ For any participant requesting early termination from the study, follow all assessments specified here, Visit 301.

⁵ Includes assessment of change in adverse events and concomitant medications. Changes should be recorded in eCRFs as appropriate.

⁶ Complete following the performance of each liver function test assessment done outside of a transplant center clinical visit; AEs and concomitant medications to be reviewed.

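### Acute and chronic rejection are each pooled over ITT without regard to who has scheduled biopsies, so silent chronic rejection in taper failures can be missed and counted as no event

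*SAP*

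**What the plan says.** **Incidence.** SAP 7.3, Table 7-2, gives each rejection type a crude proportion with an exact 95% interval, in ITT and PP. For acute rejection: "Incidence will be measured as the proportion of participants who have acute rejection (per Banff criteria". For chronic rejection: "Incidence will be measured as the proportion of participants who have chronic rejection (per Banff criteria". The protocol's sample size section (9.3) fixes the ITT denominator: "enrollment will continue until 60 participants who meet eligibility criteria are enrolled and initiate immunosuppression withdrawal".

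**Timing.** For all rejection types, Table 7-2 says "timing will be expressed as the time from the initiation of immunosuppression withdrawal to the time of the first biopsy showing acute rejection", summarized descriptively. The mock safety table in the SAP appendix has a Total column only and one median (IQR) per type, including a time to first chronic rejection. It has no split by biopsy source or follow-up schedule, and no count of participants biopsied.

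**Who is biopsied.** After baseline, protocol biopsies appear only in Appendix 2, at weeks 52 and 156, for participants who completed withdrawal. Section 6.10.1 gives their purpose: "These biopsies will be used to monitor liver function, to screen for subclinical rejection, and for mechanistic analyses". Others follow a different schedule. Section 6.8: "Participants who experience biopsy-confirmed rejection or presumed rejection prior to completing immunosuppression withdrawal will undergo safety follow-up per Appendix 3". Appendix 3: "The assessments outlined in Appendix 3 should be completed for all participants who initiated but did not complete immunosuppression withdrawal". Appendix 3 has no biopsy row, but its footnotes provide for a for-cause biopsy.

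**The concern.** Two groups with different chances of detection share one denominator. In completers, rejection can be found by for-cause biopsy or by a planned biopsy that needs no liver-test signal. In taper failures, only the first route exists. The protocol does not treat liver tests as a full substitute for histology. Section 3.4 notes that "subclinical rejection with normal liver function tests has also been reported in some patients". After a treated rejection, resolution is judged on ALT or GGT (6.8), a repeat biopsy is at the investigator's discretion in mild and in milder moderate cases, and the post-rejection visit in Appendix 5 has no biopsy.

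The risk is that a low ITT proportion is read as the chronic rejection rate after attempted withdrawal, when part of the denominator had no planned histology after baseline. Chronic rejection also enters the stopping-rule composite in protocol 3.5, so under-detection would carry into that count.

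Timing raises a smaller, related problem: a rejection seen only on a protocol biopsy is dated to the scheduled visit, not to its onset.

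**Working it through.** **1. The plan's own figure.** The documents state no expected chronic rejection rate. The interval method can be checked on protocol 9.3. The exact limits are the Beta quantiles B(0.025; x, n−x+1) and B(0.975; x+1, n−x). For 24/60 this gives 27.56–53.46% and for 36/60 it gives 46.54–72.44%, matching the stated (27.6, 53.5) and (46.5, 72.4). No stated figure is wrong; the issue is detection and denominator.

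**2. Routes to detection.**

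| Group | Liver tests and for-cause biopsy | Scheduled biopsy after baseline |
|---|---|---|
| During taper | yes | none |
| Completed withdrawal (Appendix 2), including later rejectors | yes | weeks 52 and 156 |
| Failed during taper (Appendix 3) | yes | none |

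**3. Direction.** Let C be the number of completers, qC and qN the true chronic rejection rates in completers and non-completers, and s the share of non-completers' cases that for-cause biopsy finds. Assume that all completers' cases are found.

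- True ITT proportion = [C·qC + (60−C)·qN]/60
- Expected reported proportion = [C·qC + s·(60−C)·qN]/60
- Shortfall = (1−s)(60−C)·qN/60, which is never negative

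The unknown qN sets the size, not the sign, provided that the central read gives no false positives.

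**4. Illustrative size.** C, q and s are assumptions. Protocol 1.3.2 expects about 30–40% successful weaning, which is 18–24 of 60; completers may be more numerous, so 36 is shown too. With qC = qN = 10%, the expected figure is 0.10·[C + s(60−C)]/60:

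| C | s = 0 | s = 0.5 | s = 1 |
|---|---|---|---|
| 18 | 3.0% | 6.5% | 10.0% |
| 24 | 4.0% | 7.0% | 10.0% |
| 36 | 6.0% | 8.0% | 10.0% |

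For C = 24 and s = 0.5: 0.10·(24 + 18)/60 = 7.0%.

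**5. Denominator.** If two chronic rejections were found, both in completers, the ITT row would show 2/60 = 3.3% (0.4–11.5). With 24 completers all biopsied, the proportion would be 2/24 = 8.3% (1.0–27.0).

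**6. Dating of protocol-biopsy events.** Withdrawal takes 24–45 weeks and the biopsy window is ±4 weeks. Counted from the start of withdrawal, the week-52 biopsy falls between 24+52−4 = 72 and 45+52+4 = 101 weeks. The week-156 biopsy falls between 24+156−4 = 176 and 45+156+4 = 205 weeks, or as late as 45+156+26 = 227 under the COVID-19 window.

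**7. Effect on pooled incidence and timing.** This is a simulation of 3,000 runs per scenario on assumed inputs:

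- All taper failures reject, uniformly over weeks 3–36.
- Completion is uniform over weeks 24–45.
- 20% of completers reject clinically in the following year.
- 5, 10 or 15% have subclinical rejection at each protocol biopsy.
- There are 24, 30 or 36 completers.

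| Completers, subclinical rate | Incidence, for-cause → pooled | Median weeks | 75th percentile, weeks |
|---|---|---|---|
| 30, 10% | 60% → 67% | 22.7 → 25.1 | 32 → 41 |
| 36, 15% (most extreme) | 52% → 65% | 24.2 → 29.4 | 36 → 69 |

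Across the nine scenarios pooled incidence rises by 3–13 points and the median by about 1–5 weeks.

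**The case against.** A reader might infer that taper failures are declared free of chronic rejection without being examined. The documents do not support that. Appendix 3 schedules liver tests every 4, then 8, then 12 weeks. Section 6.6.1 makes a for-cause biopsy mandatory when unexplained dysfunction lasts more than 72 hours. After a rejection, Appendix 5 adds center visits every 13 weeks until liver tests normalize. All biopsies are read centrally. What can be missed is rejection that stays below the liver-test threshold. Nor does the gap cover every failure: those who complete withdrawal and then reject, or fail on Table 1 histology, stay on Appendix 2 and keep their scheduled biopsies.

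A reader might also infer that acute rejection incidence and timing mainly follow the biopsy calendar. They do not. Liver tests are done every 2–3 weeks during taper and every 4 weeks for the next 26, and even the assumed scenarios move the median little.

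Two further objections stand. The simulation inputs are not in the documents, and some taper failures will not have rejected at all (3.1.3.5). The SAP plans no subgroup or cross-trial comparison of rejection, and the primary endpoint is untouched.

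One objection does not stand: that the direction of bias is open because non-completers' true rate is unknown. Step 3 shows that this rate affects only the size.

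**Conclusion.** The point holds in a limited form. The ITT chronic rejection proportion combines participants with and without planned histology, and it can only be too low if silent cases are missed in taper failures. The size is not known from the documents. The 4%, 7% and 10% figures illustrate an assumed 10% true rate with 24 completers and are not estimates. For acute rejection the effect on the median is small; timing matters mainly for the upper quartile and for subclinical or chronic rejection dated to a scheduled visit.

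Two defects in the timing rule need no assumptions. First, Table 7-2 times every rejection type to the first biopsy showing acute rejection, whereas the mock table reports time to first chronic rejection. Second, protocol 9.2.2 plans Kaplan-Meier with censoring for time-to-event endpoints, whereas the SAP uses an uncensored descriptive summary, and no text appears under its section 11 on changes from the protocol.

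This is an inexpensive reporting improvement that should be made before the tables are final. It does not invalidate the safety analysis.

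**What to change.** In SAP Table 7-2 and the mock safety table:

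- Keep the existing ITT and PP rows.
- Add rows for acute and for chronic rejection by biopsy source: for-cause, with the ITT denominator; and protocol biopsy at weeks 52 and 156, each with the number actually biopsied as denominator.
- For chronic rejection, add the number with any later post-baseline central-read biopsy by follow-up schedule (Appendix 2 or 3), fixing the time origin that defines later. Label Appendix 3 participants without one as not assessed by biopsy.
- Time chronic rejection to the first biopsy showing chronic rejection.
- Present timing by Kaplan-Meier with censoring, as in protocol 9.2.2, showing for-cause and protocol-biopsy detections separately. If the descriptive summary is kept instead, record the change in SAP section 11.

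All of this uses data already collected and asks for no additional biopsies or change in care. The cost is a few table rows, with smaller denominators and wider intervals in the protocol-biopsy rows.
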